4 STUDY POPULATION

4.1 Sample Size

Approximately 200 subjects will be enrolled in the study to obtain 160 evaluable subjects (i.e., those who receive at least 4 weeks of IMP and a cumulative radiation dose of at least 50 Gy).

Approximately 60 sites in the United States and Europe will participate in the study.

4.2 Inclusion Criteria

Subjects will be included in the study if they are or have:

- Willing and able to understand and sign the study specific Informed Consent Form (ICF) approved by the site's Institutional Review Board (IRB)/Independent Ethics Committee (IEC)
- 2. Pathologically-confirmed squamous cell carcinoma of the oral cavity, oropharynx, nasopharynx or hypopharynx or unknown primary HPV-positive tumor presumed to be of oropharyngeal, nasopharyngeal or hypopharyngeal origin.
- 3. Tumor HPV status established
- 4. Planned to receive either primary or post-operative CRT
- 5. Planned IMRT as single daily fractions of 2.0 to 2.2 Gy with a cumulative radiation dose of at least 50 Gy and maximum dose of 72 Gy
- 6. The radiation field must provide for a minimal cumulative dose of 50 Gy to at least two sites at risk for OM (maxillary or mandibular labial mucosa, right or left buccal mucosa, right or left ventral and/or lateral tongue, floor of oral cavity, or soft palate/tonsillar pillars)
- 7. Planned administration of cisplatin administered at a dose of 30 to 40 mg/m² weekly during RT or tri-weekly 80 to 100 mg/m² days 1, 22 and 43
- 8. Males or females 21 years or older
- 9. Karnofsky performance score (KPS) ≥ 70% (appendix E)
- 10. Screening laboratory assessments:
 - Hemoglobin ≥ 10g/dl

This document contains confidential information. It is intended solely for the use of the principal investigator, co-investigators, staff, appropriate institutional review boards or ethical committees, and other required regulatory bodies.

- White blood count ≥ 3500 cells/mm3
- Absolute neutrophil counts ≥ 1500 cells/ mm3
- Serum AST and ALT \leq 3 x ULN
- Calculated Creatinine Clearance ≥ 50 ml/min

• Negative pregnancy test (serum or urine)[#] performed 7 days before IMP administration

11. Females of childbearing potential[#] must confirm the use of an effective method of birth control during study participation and for 30 days following the last treatment with IMP. Acceptable methods of contraception for females include the following:

a) Double contraceptive methods including the use of either a male or female condom, a diaphragm or cervical cap associated with a spermicide, on top of one of the following:

- combined estrogen and progestogen containing hormonal contraception (oral, intravaginal or transdermal)
- Progestogen-only hormonal contraception associated with inhibition of ovulation (oral, injectable, implantable)
- Intrauterine device
- Intrauterine hormone-releasing system
- b) Vasectomized partner
- c) Sexual abstinence^{\$}

Male subjects, when having hetero-sexual intercourse with a female of childbearing potential[#], must use a condom during study participation and for 90 days following the last treatment with IMP. For non-pregnant female partner of childbearing potential[#] the contraception recommendations as described above should also be considered for 90 days after the last treatment with IMP of their male partner.

[#]A female is considered of childbearing potential, i.e. fertile, following menarche and until becoming post-menopausal unless permanently sterile. Permanent sterilization methods include hysterectomy, bilateral salpingectomy and bilateral oophorectomy. A postmenopausal state is defined as no menses for 12 months without an alternative medical cause.

^{\$}Sexual abstinence is defined as refraining from heterosexual intercourse during the entire period of risk associated with the study treatment. The reliability of sexual abstinence needs to be evaluated in

This document contains confidential information. It is intended solely for the use of the principal investigator, co-investigators, staff, appropriate institutional review boards or ethical committees, and other required regulatory bodies.

relation to the duration of the clinical trial and the preferred and usual lifestyle of the subject. Periodic abstinence (calendar, symptothermal, post-ovulation methods) is not an acceptable method of contraception.

4.3 Exclusion Criteria

Subjects will be excluded from participation in the study if they are or have:

- 1. Prior radiation to the head and neck
- 2. Increased risk of developing infectious endocarditis (American Association of Endodontists, 2017):
 - Prosthetic cardiac valves, including transcatheter-implanted prostheses and homografts
 - Prosthetic material used for cardiac valve repair, such as annuloplasty rings and chords
 - Previous Infectious Endocarditis
 - Unrepaired cyanotic congenital heart disease or repaired congenital heart disease, with residual shunts or valvular regurgitation at the site of or adjacent to the site of a prosthetic patch or prosthetic device
 - Cardiac transplant with valve regurgitation due to a structurally abnormal valve
- 3. Prior gene therapy
- 4. Presence of active infectious oral disease
- 5. Presence of any oral lesions that may confound the ability to assess oral mucositis grade
- 6. Current use of antibiotic rinses or troches
- 7. Herbal, alternative remedies, and alcohol containing over-the-counter mouthwashes are excluded during the course of the study.
- 8. Current alcohol abuse syndrome
- 9. Chronic immunosuppression
- 10. Known seropositive for HIV

This document contains confidential information. It is intended solely for the use of the principal investigator, co-investigators, staff, appropriate institutional review boards or ethical committees, and other required regulatory bodies.

- 11. Use of investigational agent within 30 days of signing informed consent
- 12. Tooth extraction prior to radiation in which the extraction site is not epithelialized (typically within 5-10 days after extraction)
- 13. Signs and symptoms of active dental disease including toothache, severely mobile teeth, draining intraoral fistula(e), intraoral swelling (not associated with the primary tumor), gingival suppuration, gross caries, or fractured teeth involving the pulp
- 14. Female subjects who are pregnant or nursing
- 15. Known allergy to excipients of the IMP, such as sodium glutamate, sorbitol, dextrin (from maize starch), anhydrous glucose, phosphate buffers salts and mannitol
- 16. Inability to give informed consent or comply with study requirements
- 17. Unwilling or unable to complete subject diary
- 18. Any other clinical condition, psychiatric condition or prior therapy that, in the opinion of the Investigator, would make the subject unsuitable for the study or unable or to comply with follow-up visits

4.4 Removal of Subjects

In accordance with the Declaration of Helsinki, subjects have the right to withdraw from the study at any time for any reason. The Investigator and Sponsor also have the right to withdraw subjects from the study. Subjects may be removed from the study for the following reasons:

- Adverse experiences
- At the request of the Investigator or Sponsor, whether for administrative or other reasons
- Protocol violation or unreliable behavior
- Termination of the study by the Sponsor
- Symptoms suggesting clinically significant bacteremia that can be attributed to sAGX00085 (as determined by 3 consecutive blood cultures) (see section 6.2 Safety Assessments and 8.4 Recording of Adverse Events)

This document contains confidential information. It is intended solely for the use of the principal investigator, co-investigators, staff, appropriate institutional review boards or ethical committees, and other required regulatory bodies.

The date for a subject who discontinues and the reason for discontinuation will be recorded in the electronic case report form (eCRF). A complete listing of subject disposition (including subject discontinuation from the study and the reason for discontinuation), any concomitant medications required (including route, duration, and frequency of administration), and protocol deviations during the study will be provided in the study report.

If a subject discontinues all end of active treatment phase procedures should be conducted. If a subject expresses a desire to discontinue the study after completing a period, the investigator will make all efforts to complete the end of active treatment phase procedures.

If a subject is removed from the study, the date of the last dose of IMP and all observations collected up to the time of termination will be recorded on the eCRF along with the reason for termination. Scheduled safety evaluations and follow-up examinations will be conducted, if possible.

When a subject fails to return for scheduled assessments, the following efforts should be made to contact him/her to determine a reason for the failure to return: three phone attempts, including the date and time, should be documented in the subject's source documents. If there is no response to the phone calls, a certified letter should be sent to the subject. After these efforts have been exhausted, a subject should be identified as lost to follow-up in the eCRF.

5 STUDY TREATMENT

5.1 Radiation Therapy Treatment Plan

Subjects will receive a continuous course of intensity-modulated radiotherapy (IMRT) with a minimum cumulative dose of 50 Gy and maximum dose of 72 Gy. Planned radiation treatment fields must include at least 2 at-risk sites for oral mucositis (maxillary or mandibular labial mucosa, right or left buccal mucosa, right or left ventral and/or lateral tongue, floor of oral cavity, or soft palate/tonsillar pillars) with each site receiving a total dose of \geq 50 Gy.

Radiation dose delivery will be clearly documented.

Changes in the radiation therapy plan will be allowed. However, the changes (example: dose delay, changes in the planned radiation dose or number of fractions) and the reason for the change should be clearly documented.

This document contains confidential information. It is intended solely for the use of the principal investigator, co-investigators, staff, appropriate institutional review boards or ethical committees, and other required regulatory bodies.

5.2 Chemotherapy Treatment Plan

Subjects will receive monotherapy with cisplatin administered at a dose of 30 to 40 mg/m² weekly during RT or tri-weekly 80 to 100 mg/m² days 1, 22 and 43.

The use of cisplatin concurrently with radiotherapy is in agreement with standard, current guidelines for the treatment of squamous cell carcinoma of the oral cavity and oropharynx (NCCN Guidelines Insights 2018; Head and Neck Cancers, Version 1.2018; Quon et al., 2017; Gregoire et al., 2010)

Chemotherapy dose and schedule will be documented.

Changes in the chemotherapy agent, dose or schedule due to treatment related toxicity will be allowed. However, the reason for the change must be clearly documented.

5.3 Investigational Medicinal Product Treatment Plan

Investigational Medicinal Product (IMP) will be applied three times daily beginning on the first day (Day 1) of CRT (CT or RT whatever comes first) and continuing for two weeks (14 days) following the last day of CRT.

5.4 Identity of Investigational Medicinal Product

AG013 is composed of a recombinant *Lactococcus (L.) lactis* strain sAGX0085, engineered to secrete hTFF1. The AG013 Drug Substance (AG013-DS) is an amorphous, slightly yellow, lyophilized powder, at a concentration of not less than (NLT) 6.4 x 10^{11} CFU/g *L. lactis* sAGX0085.

AG013-DP consists of AG013-DS, mixed with appropriate excipients and is presented as a 770 mg powder for reconstitution.

The bulk DP is formulated to reach a final strength of 2.6×10^{11} CFU/g of *L. lactis* sAGX0085.

Subjects assigned to the placebo group will receive appearance- and taste-matched placebo powder.

The clinical formulation of AG013 is an oral, topical administration in the form of a MR. This MR suspension is prepared by reconstitution of the AG013-DP/Placebo into a selected SR solution, packed in individual glass bottles, to form the MR suspension prior to administration.

This SR is an aqueous solution containing glucose (dextrose), phosphate buffer salts (pH buffer) and saccharin sodium (sweetener) and a raspberry aroma in purified water.

This document contains confidential information. It is intended solely for the use of the principal investigator, co-investigators, staff, appropriate institutional review boards or ethical committees, and other required regulatory bodies.

The final concentration of AG013 in the oral rinse is 2.0×10^{11} CFU/15 ml.

The AG013-DP/Placebo components of the mouth rinse formulation should be stored refrigerated (2°C to 8°C; 35°F to 47°F) in their original package. The SR solution can be stored at room temperature (15°C to 25°C; 59°F to 77°F) in their original package. The IMP must be kept in a secure area at the study site.

5.5 Labeling and Packaging

AG013-DP and placebo will be presented as a compressed powder in 30 ml clear glass bottles. The AG013-DP and placebo bottles will be placed in an aluminum sachet. The reconstitution solution will be delivered in a 15 ml dark glass bottle.

Labeling of the study treatment will conform to all requirements specified by governing regulations. Label directions will specify that the study drug should be stored refrigerated or at room temperature.

5.6 Investigational Medicinal Product Administration

Subjects will receive a mouth rinse package which will contain the following 2 components for the reconstitution of the mouth rinse suspension:

- AG013-DP powder or matching placebo in an aluminum sachet
- Reconstitution solution

A short summary of dose preparation is provided in Figure 2.

Figure 2 Summary of the different steps to reconstitute the mouth rinse suspension

Briefly, the SR needs to be added to the AG013-DP or Placebo, and shaken for at least 30 seconds to obtain a homogeneous white opaque suspension, ready for use.

Subjects will mix the study medication. Then, prior to the administration of the study medication, the patient will complete a 30 second cleansing rinse using bottled water. After

This document contains confidential information. It is intended solely for the use of the principal investigator, co-investigators, staff, appropriate institutional review boards or ethical committees, and other required regulatory bodies.

completing the cleansing rinse, subjects will shake the study medication to ensure reconstitution of the powder and then dose. Subjects will rinse with the suspension for 30 seconds three times each day using the assigned IMP. The suspension should then be expectorated into a sink or toilet. Subjects must have a witnessed dose; the first dose on Day 1 of CRT (prior to CT or RT whatever comes first). The witnessed dose should occur after the subject completes the OMDQ and prior to the subject leaving the clinic.

The IMP should be administered after meal however subjects should not eat, brush their teeth or use mouthwash for 15 minutes prior to and for 90 minutes after dosing. In addition, subjects should refrain from using processed sugars (e.g., candy, soft drinks, etc.) for 90 minutes after dosing with the study medication. Throughout participation in the study (i.e. till end of short term follow-up phase), subjects should be instructed not to drink alcohol within at least 4 hours after dosing with IMP or chew any gum other than the gum provided in the caries prevention kit (Section 5.15). Subjects should also be directed to only use the gum per the caries prevention instructions.

Detailed instructions for dose preparation and dispensing to subjects will be provided to the clinical site by the Sponsor or its designee.

5.7 IMP Accountability

The Investigator or his/her designee is responsible for ensuring adequate accountability of all used and unused IMP. This includes acknowledgement of receipt of each shipment of IMP (quantity and condition), subject dispensing records and returned or destroyed IMP. Dispensing records will document quantities received. Quantities dispensed to subjects will be documented, including lot number, date dispensed, subject identification number, subject initials and the initials of the person dispensing the IMP.

Throughout the course of the study, the Sponsor or its designee will perform IMP accountability and provide instructions for adequate IMP disposal. IMP accountability records must be readily available for audit by the Sponsor or its designee and for inspection by regulatory authorities at any time.

The Investigator will not allow IMP to be given to any subject not included in the study or any unauthorized person.

It is the responsibility of the site personnel to maintain adequate IMP dispensing records.

5.8 Compliance

IMP compliance will be reviewed by the study staff at the weekly visits during the active treatment period. Each subject will be instructed to return all used and unused bottles at each weekly dispensing visit during the active treatment period and at the End of Active

This document contains confidential information. It is intended solely for the use of the principal investigator, co-investigators, staff, appropriate institutional review boards or ethical committees, and other required regulatory bodies.

Treatment Phase Visit. A count of the used and unused bottles remaining in the mouth rinse package will be performed to assess compliance.

5.9 Method of Assigning Subjects to Treatment

Subjects who meet all inclusion and exclusion criteria will be centrally randomized 1:1 to receive placebo three times per day or AG013 three times per day. Each subject's treatment assignment will be stratified based on cisplatin schedule (weekly versus tri-weekly), and by HPV status (positive versus negative) and geographic region (US versus Europe). Dynamic randomization will be used for patient randomization in this study. A randomization number and associated treatment assignment will be made using an interactive web response system (IWRS).

5.10 Selection of Doses

In this Phase 2 study, a single dose of IMP will be administered at a dose frequency of three times daily. The selection of dose frequency is based on the intention to assess safety and tolerability of a dose frequency that is anticipated to be clinically efficacious while maximizing patient compliance. The dosing frequency selection is based on trends noted in the Phase 1b trial and PK results of the Phase 1 PK study in healthy volunteers.

The Phase 1 PK study in healthy volunteers demonstrated that live AG013 bacteria adhered to the buccal mucosa and actively secreted hTFF1 in situ. A homogeneous exposure of live AG013 bacteria to the entire mucosal surface was seen. The exposure to AG013 and hTFF1 was significantly reduced by food intake but not by beverage intake. Therefore, in order to maximize efficacy and compliance AG013 should be dosed after meal intake (3 times daily) to ensure optimal exposure and hTFF1 delivery. Three rinses of AG013 result in a clinically relevant 24 hour exposure period of AG013.

The dose per mouth rinse in the proposed Phase 2 study is $2x10^{11}$ CFU or $2.8x10^9$ CFU/kg BW which is similar to the dose used in the Phase 1b trial AG013-ODOM-101 and Phase 1 PK study AG013-CSD-MU-004 in healthy volunteers.

5.11 Blinding (if applicable)

Blinding will be accomplished by arranging for AG013 and placebo components to have identical packaging. IMP will be delivered in a blinded fashion, as outlined in the Pharmacy Manual. All study personnel at the site, the patient and the Sponsor will be blinded to treatment allocation for the duration of the study.

Code-breaking will be organized and logged via the central randomization system, i.e. IWRS. In case of a medical emergency, the investigator can immediately obtain the identity of IMP assigned to subject numbers or to individual boxes of IMP by access through the IWRS.

This document contains confidential information. It is intended solely for the use of the principal investigator, co-investigators, staff, appropriate institutional review boards or ethical committees, and other required regulatory bodies.

In the event that the blind is broken, the Principal Investigator should contact the medical monitor or his/her designee at the contact numbers provided to the site. A subject's treatment assignment should only be unblinded when knowledge of the treatment is essential for the further management of the subject (i.e., medical emergency).

Where the blind is broken the patient should immediately be withdrawn from the study and IMP should immediately be discontinued.

The reason and date/time of the unblinding and the name of the individual who broke the blind must be appropriately documented in the subject's medical record or source documents and in the eCRF.

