6.3 Efficacy Assessments

6.3.1 OM Assessments

OM assessments will be completed at the screening and baseline visit, twice weekly (no less than 48 hours apart) within each 5-day RT during the active treatment phase, at the end of active treatment visit, and weekly for four weeks during the short term follow-up phase. If OM has not decreased to less than grade 2, weekly OM assessments will continue until OM is a grade 1 or less.

OM will be assessed by a treatment-blinded, trained evaluator and scored using WHO mucositis criteria. If a subject withdraws prior to the end of the active treatment phase for any reason, a complete oral assessment must be done on that day.

Specific on-line training (6 modules) and instructions regarding oral mucositis assessment performance, grading and documentation will be provided to the clinical site by the Sponsor or its designee. Designated trained study staff (oral evaluators) will conduct all assessments using a standardized and consistent method. Completion of training for Modules 4 and 5 (Armamentarium and examination technique and Evaluation and worksheet completion) shall be performed by oral evaluators no more than 4 weeks prior to the first study subject assessment.

Oral evaluators should have one of the following qualifications: Medical Doctor (MD), Doctor of Osteopathic Medicine (DO), Doctor of Medicine in Dentistry (DMD), Doctor of Dental Surgery (DDS), Registered Nurse (RN), Nurse Practitioner (NP), Registered Dental Hygienist (RDH) (or European equivalents) or Physician Assistant (PA) To reduce inter-observer variability, as few oral evaluators as possible should be involved in the assessments of an individual subject. To the fullest extent possible the same observer should rate the same subjects OM. The oral evaluators will use a Sponsor-provided headlamp for all oral assessments conducted for this study.

The WHO grade will be the primary measure for assessing OM. The assessment of the impact of OM on a subject's ability to eat is critical for accurate scoring of the WHO scale. Therefore, standardization of the assessment is very important. In order to reduce variability in assessing food intake, definitions for solids, liquids and nothing by mouth are below:

- Solid foods are defined as foods that need to be chewed. Examples include: meat, grains and vegetables

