10.3.2 Intent-to-Treat (ITT) Population

The ITT population will include all randomized subjects. Subjects will be analyzed according to the treatment group to which they are randomized, regardless of treatment actually received. This population will serve as the basis for the primary efficacy analysis.

A modified ITT (mITT) population, defined as all ITT subjects who receive IMP and have postbaseline efficacy data, will be used for all primary and secondary efficacy endpoints.

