8.7 EFFICACY ENDPOINTS AND ANALYSIS

8.7.1 ANALYSIS OF PRIMARY EFFICACY ENDPOINT

The duration of severe OM (WHO grade 3 or 4) will be calculated as the number of days from the onset of severe OM (first time a WHO grade 3 or 4 is observed) to the day when severe OM has resolved (first time WHO grade 2 or less is observed after last WHO grade 3 or 4). This calculation allows for fluctuation in severity grades and considers separate episodes of SOM to be additive. Durations of 0 will be assigned to subjects who do not experience severe OM, even if the subject was not followed for the full planned period. Any subject who dies or withdraws prior to resolution of severe OM (i.e., with grade 3 or 4 at last assessment) will be assumed to have severe OM for the remainder of the observation period. In these cases, duration will be calculated as the number of days from the first onset of severe OM (WHO grade 3 or 4) until the end of Short Term Follow-up phase which will be taken as Week 13 (Day 91 relative to start of CRT). All available OM assessments will be used to derive efficacy endpoints, including WHO grades recorded during the treatment phase and the short-term follow-up period.

The intent of the primary statistical analysis is to test the superiority of AG013 over placebo in reducing the duration of severe OM. The null hypothesis is that the AG013 and placebo groups have the same duration (in days) of severe OM. The alternative hypothesis is that the duration of severe OM in the two treatment groups is different.

The generalized CMH method, stratified by cisplatin regimen (weekly versus tri-weekly), by HPV status (positive versus negative) and region (US versus Europe), will be used for the primary efficacy analysis. In case of erroneous stratification at baseline, the corrected stratification data will be used for the analysis. Standardized mid-ranks (also known as modified ridit scores) will be used for the test statistic. This generalized CMH test follows a chi-square distribution with 1 degree of freedom. The efficacy analysis will be performed in the ITT, mITT, and PP populations, with the ITT designated as primary. Below is the sample code that performs this analysis:

```
proc freq
```

```
data=test;
tables STRATUM*TRTPN*OM_DURATION / CMH SCORE=MODRIDIT;
run;
```

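### Breaking the blind ends study follow-up as well as study drug, so later mucositis grades and tumor status can be lost although the primary analysis is ITT

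*Protocol*

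**What the plan says.** Protocol 5.11 limits code-breaking to medical emergencies in which the assignment must be known to manage the subject. It then says: "Where the blind is broken the patient should immediately be withdrawn from the study and IMP should immediately be discontinued."

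The primary population is ITT. Protocol 10.3.2: "The ITT population will include all randomized subjects" and "Subjects will be analyzed according to the treatment group to which they are randomized, regardless of treatment actually received." SAP 7.2 agrees.

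For removed subjects, Protocol 4.4 provides three things:
- data to date are kept: "all observations collected up to the time of termination will be recorded on the eCRF"
- a closing set of procedures: "If a subject discontinues all end of active treatment phase procedures should be conducted"
- later visits, conditionally: "Scheduled safety evaluations and follow-up examinations will be conducted, if possible"

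Protocol 6.3.1 adds that, on withdrawal before the end of active treatment, "a complete oral assessment must be done on that day."

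SAP 8.7.1 sets the primary-endpoint rule for "Any subject who dies or withdraws prior to resolution of severe OM," which it defines as a grade of 3 or 4 at the last assessment. Severe OM is then assumed to continue to Day 91. Protocol 10.5 ends the same imputation two weeks after the last planned CRT dose. SAP section 9, which lists departures from the protocol, does not mention this change.

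**The concern.** An ITT comparison needs outcomes after study drug stops, whatever the reason for stopping. The blinding section ends participation itself at the code-break. No section firmly requires the twice-weekly and weekly OM grades, or tumor status at 3, 6 and 12 months, to continue afterwards.

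Two other rules sit awkwardly beside this one. Protocol 5.13 keeps subjects who take prohibited therapies in the study. Protocol section 9 unblinds the study at the first database lock, before the last subjects finish 12-month tumor follow-up, so tumor assessment after unblinding is already accepted. Tumor response is a safety endpoint, and long-term follow-up exists to show that AG013 does not harm it.

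The missing data may not be random, because code-breaks follow medical emergencies. Grades that could have been observed would be replaced by a rule, and the rule can move the result in either direction.

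**Working it through.** **1. Plan figures used for scale.** The plan gives no number of code-breaks. Enrolment reproduces: 1 − 160/200 = 20% non-evaluable, and 160/(1 − 0.20) = 200, or 100 per arm. The planning difference is 5 days with SD 10.8 (Protocol 10.2). With 80 per arm and a two-sided 5% t-test, this gives 82.9% power against the stated approximately 80%. That figure is not in dispute here.

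**2. What happens to a withdrawn subject with no later grades (SAP 8.7.1 and 8.7.2).**
- Last grade 3 or 4: severe OM is assumed to Day 91.
- Never severe: 0 days, even if follow-up was incomplete. The subject is also censored for time to onset and counts as a non-event for incidence, because SAP section 9 drops the protocol's worst-case rule for incidence.
- Severe and resolved: the observed duration stands.

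**3. Size of the long imputed value.** Imputed duration = end day − onset day. The SAP end day is 91, which matches a 9-week active phase plus 4 weeks (63 + 28). The Protocol end day is the end of the 7- to 9-week active phase, Day 49 to Day 63. Onset days are assumed.

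| Onset day (assumed) | SAP rule, days | In SDs of 10.8 | Protocol rule, 7-week to 9-week phase, days |
|---|---|---|---|
| 21 | 70 | 6.5 | 28 to 42 |
| 28 | 63 | 5.8 | 21 to 35 |
| 42 | 49 | 4.5 | 7 to 21 |
| 49 | 42 | 3.9 | 0 to 14 |

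For a 7-week phase, short-term follow-up ends at about Day 49 + 28 = 77. The SAP rule can therefore run 91 − 77 = 14 days past planned follow-up.

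**4. Effect on an arm mean.** Shift per subject = (imputed − true)/100. No true duration is given, so 10 to 30 days is assumed, with onset on Day 28.
- SAP rule: (63 − 10)/100 = 0.53 to (63 − 30)/100 = 0.33 day, or 11% to 7% of the 5-day target.
- Protocol rule: from (21 − 30)/100 = −0.09 to (35 − 10)/100 = 0.25 day.
- Scored 0 when the true duration would have been 10 to 30 days: −0.10 to −0.30 day.

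**5. Effect on a rank test.** The primary test is CMH on modified ridits, so a mean shift is not its metric. An illustrative simulation used an unstratified rank test with 100 per arm. Durations were an assumed zero-inflated gamma: incidence 75% against 55%, mean 17.5 against 15.5 days when present, SD about 10.3, mean difference about 4.7 days. Base power was about 89%. Randomly chosen subjects were then overwritten.

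| Overwritten value | 1 subject | 3 subjects | 5 subjects |
|---|---|---|---|
| 42 to 70 days, each arm | 89% | 86% | 84% |
| 42 to 70 days, AG013 arm only | 87% | 79% | 69% |
| 0 days, AG013 arm only | 91% | 93% | 94% |

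The overwritten subjects came from the whole arm, including those with no severe OM, so the losses from long values are larger than the SAP rule itself would produce. The table shows direction and rough scale only.

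**The case against.** The strongest defense is that the protocol already softens the rule. The subject is not removed from ITT, earlier data are kept, an oral assessment is required on the day of withdrawal during active treatment, end-of-phase procedures are requested, and SAP 8.7.1 uses every available grade, so later grades count if collected. All of this stands. A reader might infer that the rule discards a subject's ITT data; the documents do not support that. What remains is that the later visits are conditional and that section 5.11, read alone, tells the site the subject has left.

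A reader might also infer that withdrawal always forces an extreme duration. It does not: the Day 91 rule needs a grade of 3 or 4 at the last assessment, and a resolved episode keeps its observed length. The 63-day illustration also owes much to the SAP's end date, which applies to every unresolved withdrawal and not only to code-breaks.

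SAP 8.7.1 plans a sensitivity analysis that replaces both kinds of imputed value with same-arm medians. That helps to judge robustness, but it cannot recover grades never collected.

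Finally, code-breaks are restricted to emergencies, ranks bound the influence of long values, and continued grading may involve staff who know the assignment. These points limit the size of the problem and name a real cost. They do not explain why follow-up should end.

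**Conclusion.** The point holds as a low-cost improvement. As written, section 5.11 can lose OM grades and tumor status after a code-break that the ITT analysis and the tumor safety endpoint would use, and section 4.4 only partly offsets this. With an assumed onset on Day 28, an unresolved subject's imputed duration is 63 days under the SAP and 21 to 35 days under the Protocol; a never-severe subject scores 0.

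The total effect cannot be computed, because the documents state no number of code-breaks; it is probably small. Onset days, true durations and the simulated distribution are assumptions. A reader might infer that code-breaks will cluster in the AG013 arm, since Protocol Appendix H names bacteremia and sepsis as potential events of the study drug regimen. Imbalance is possible, but nothing in the documents shows it, and the bias could favor either arm.

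**What to change.** Leave the instruction on study drug in Protocol 5.11 unchanged. Replace the withdrawal from the study with a statement that, after a code-break, the subject remains in follow-up for all scheduled OM, safety and tumor assessments if consent continues. Bring section 4.4 into line, so that these visits are expected and not merely attempted.

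Add that the oral evaluator stays blinded where possible, that assessments by staff who know the assignment are flagged, and that observed grades are used in the ITT analysis. Separately, reconcile the imputation end dates in Protocol 10.5 and SAP 8.7.1, and list the outcome in SAP section 9 if they still differ.

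The cost is protocol and SAP wording plus visits already in the schedule. The downside is that a few OM grades may come from staff who know the assignment; the flag lets their influence be checked.
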